**Data Safety Monitoring Board (DSMB): The monitoring of this trial will be provided by MD Anderson Cancer Center DSMB**

## Visit Schedule

Table 1, below outlines the required study assessments.

**Table 1 Study Event Schedule**

	Baseline (within 60 days prior to surgery)	Day of surgical Procedure	First 48 hours after surgery	Procedures until Discharge	Procedures After Discharge
Informed Consent	X a				
Inclusion / Exclusion Criteria Assessment	X				
Demographics/ Medical History	X				

Randomization and Intent to Treat		X b			
Vital Signs	X c	X c			
Physical Examination	X				
Laboratory Tests	X d				
Data collection	X e	X e	QoR15, pain scores, opioid consumption,	QoR15, pain scores, opioid consumption, LOS	QoR15, pain scores, opioid consumption,
Adverse Events		X f	ORADE, AE, SAE, complications (Clavien-Dindo)		

a After confirmation of eligibility and 30 days after surgery.

b After confirmation of eligibility and before surgery.

c Height, weight, systolic/diastolic blood pressure, heart rate, and respiratory rate (height and weight will only be measured at baseline)

c Data will be collected from the patients standard of care lab tests. These typically include creatinine, platelet and white blood cells count, and hemoglobin and hematocrit

d Complete blood counts, routine electrolyte determinations and renal function laboratory tests collected

e ORADE: opioid related adverse effects, AE: adverse events, SAE: serious adverse events, QoR: quality of recovery, LOS: length of stay

f During surgery, at PACU discharge and POD1 and 2.

## Adverse Events

### General

All adverse events (AE) and serious adverse events (SAE) will be monitored from the time of procedure through end of the study.

An AE is defined as any undesirable clinical occurrence in a patient whether or not it is considered to be device related. In addition, the definition of AE applies to any event with an onset post study procedure or to any underlying diseases, present at baseline, that exacerbate in severity post study procedure. Therefore, an underlying disease that was present at the time of enrollment is not reported as an AE, but any increase in the severity of the underlying disease is to be reported as an AE. All reported AEs must be recorded in the database. A description of the event, including the start date, resolution date, action taken, and the outcome should be provided, along with the Investigator's assessment of the relationship between the AE, the study treatment and the study procedure. This protocol will use common terminology criteria for adverse events (CTCAE) version 4.0. For the AEs not characterized in the CTACE, the following definitions for rating severity of AEs will be used:

Mild: Awareness of signs or symptoms, but easily tolerated; are of minor irritant type; causing no loss of time from normal activities;

- symptoms would not require medication or a medical evaluation;  
signs or symptoms are transient.
- Moderate: Interferes with the patient's usual activity and/or requires symptomatic treatment.
- Severe: Symptom(s) causing severe discomfort and significant impact of the patient's usual activity and requires treatment.

A serious adverse event (SAE) is defined as an event which leads to:

- Death due to any cause
- Life-threatening condition
- Results in persistent or significant disability/incapacity
- Requires in-patient hospitalization or prolonged hospitalization
- Necessitates an intervention to prevent a permanent impairment of a body function or permanent damage to a body structure
- Results in congenital abnormality

All SAE's will be reported.

***Device-Related Adverse Event:*** Not applicable

***Procedure-Related Adverse Event:*** an adverse event is considered to be procedure-related when, in the judgment of the Investigator; it is reasonable to believe that the event is associated with the assigned study procedure. Other products, surgical techniques, or medications required specifically for the procedure are likely to have contributed to the occurrence of the event.

***Concomitant Medication-Related Adverse Event:*** Not applicable

***Pre-Existing Condition-Related Adverse Event:*** an adverse event is considered to be related to a pre-existing condition when, in the judgment of the Investigator, it is reasonable to believe that the event is associated with the patient's pre-existing condition and is not specific to the **STUDY** procedures. Pre-existing conditions that are aggravated or become more severe during or after the procedure should be evaluated on a case-by-case basis to determine if the event may be more appropriately classified as procedure-related.

The Investigator should follow all unresolved serious adverse events until the events are resolved, the patient is lost to follow-up, the patient has withdrawn consent, or the adverse event is otherwise explained.

For purposes of this study, the following events are not considered adverse events, because they are normally expected to occur in conjunction post-surgery, or are associated with customary, standard care of patients undergoing these procedures:

- Early post-operative pain (within 48hours post-index procedure) at the incision site and/or related to position on procedure table

- Post-anesthesia emesis, nausea, or headache (within 24 hours post-index procedure)
- Chest pain without associated ECG changes
- Hematocrit decrease from baseline not associated with hemodynamic changes, remaining above 30% and not requiring transfusion
- Electrolyte imbalance without clinical sequelae following endoscopic procedure, even if requiring correction
- Low grade temperature increase ( $\leq 38.3^{\circ}\text{C}/\leq 101^{\circ}\text{F}$ )
- Sinus bradycardia/tachycardia that does not require treatment or intervention
- Systolic or diastolic blood pressure changes that do not require treatment or intervention
- Any pre-planned surgical procedures

This listing of events is intended to provide guidance to the investigational sites for purposes of adverse event reporting. The Investigator at the investigational site should utilize his/her own clinical judgment in evaluating adverse experiences, and may decide that the above events should be reported as adverse events.

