## 1. STUDY SYNOPSIS

Four quadrant TAP (4Q-TAP) block with plain and liposomal bupivacaine vs. Thoracic Epidural Analgesia (TEA) in patient's undergoing cytoreductive surgery with hyperthermic intraperitoneal chemotherapy (CRS-HIPEC) on an enhanced recovery pathway: a single-blinded, randomized, non-inferiority study.
	

Objectives
	
To evaluate the impact of 4 quadrants TAP blocks (4Q-TAP) versus Thoracic Epidural Analgesia (routine care) on the quality of recovery and other clinically relevant outcomes after CRS-HIPEC surgery.
 
To study the incidence of adverse events associated with (4Q-TAP) blocks versus Thoracic Epidural Analgesia (routine care) after CRS-HIPEC surgery.

Aims
	
a. Primary Aim: To compare the efficacy of 4 quadrants TAP blocks (4Q-TAP) versus Thoracic Epidural Analgesia (routine care) on the quality of recovery 48 hours after CRS-HIPEC surgery.
 
b. Secondary Aim 1: To compare the efficacy of 4 quadrants TAP blocks (4Q-TAP) versus Thoracic Epidural Analgesia (routine of care) on postoperative pain 48 hours after CRS-HIPEC surgery.
 
c. Secondary Aim 2: To compare the total opioid consumption between patients with 4 quadrants TAP blocks (4Q-TAP) versus Thoracic Epidural Analgesia (routine care) intraoperatively and up to 48 hours after CRS-HIPEC surgery.
 
d. Secondary Aim 3: To compare the length of stay (LOS) between patients with 4 quadrants TAP blocks (4Q-TAP) versus Thoracic Epidural Analgesia (routine care) after CRS-HIPEC surgery.
 
e. Secondary Aim 4. To compare the incidence of adverse events (i.e. postoperative hypotension, failed block) related to 4 quadrants TAP blocks (4Q-TAP) versus Thoracic Epidural Analgesia (routine care) 48 hours after CRS-HIPEC surgery.
 
f. Secondary Aim 5. To compare the incidence of opioid-related adverse (i.e. respiratory depression, pruritus, sedation, delirium) events related to 4 quadrants TAP blocks (4Q-TAP) versus Thoracic Epidural Analgesia (routine care) 48 hours after CRS-HIPEC surgery.
 
g. Secondary Aim 6. To compare the incidence postoperative complications and morbidity in patients receiving 4 quadrants TAP blocks (4Q-TAP) versus Thoracic Epidural Analgesia (routine care) 48 hours after CRS-HIPEC surgery.

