
Study Design
	
This is a randomized controlled trial designed to test efficacy of 4Q-TAP against TEA (routine of care) on quality of recovery 48 hours after CRS-HIPEC surgery. All patients will be enrolled at MD Anderson Cancer Center.

Number of Patients
	
160 patients randomized to the 2 study arms (80 patients per arm)

Sites
	
MD Anderson Cancer Center

Duration of Study	It is expected that this will take up to 36 months.
Duration of Patient Participation	Patients who consented to participate in the study will remain in the study until last planned outcome is collected on postoperative day 30. Patient will have the opportunity to withdraw from the study at any time.
Primary Endpoint Definition	Quality of recovery (QoR) 48 hours after CRS-HIPEC surgery.
Secondary Endpoints	
 
• Postoperative pain 48 hours
 
• The total opioid consumption within 48 hours after surgery
 
• Length of stay
 
• Incidence of adverse events
 
• Incidence of opioid-related adverse events
 
• Postoperative complications and morbidity
 
• QoR on postoperative day 3, 7 10 and 30.
 

Primary Safety Endpoint	All reported adverse events.
Follow-Up Schedule	The study will be considered complete after all randomized patients have had 30 days of follow-up data collection.
Inclusion Criteria	
 
1. Written informed consent;
 
2. 18 years old or older;
 
3. American Society of Anesthesiologists physical status (ASA) 1-3;
 
4. Scheduled surgery: open elective CRS-HIPEC;
 
5. Able to complete the QoR 15 questionnaire;
 
6. Patients scheduled to receive intraoperative chemotherapy;
 

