## 3. STUDY AIMS

a. **Primary Aim:** To compare the efficacy of 4 quadrants TAP blocks (4Q-TAP) versus Thoracic Epidural Analgesia (routine care) on the quality of recovery 48 hours after CRS-HIPEC surgery.

**Hypothesis:** The quality of recovery with 4 quadrants TAP blocks (4Q-TAP) 48 hs after CRS-HIPEC surgery is not inferior to Thoracic Epidural Analgesia (routine care).

b. **Secondary Aim 1:** To compare the efficacy of 4 quadrants TAP blocks (4Q-TAP) versus Thoracic Epidural Analgesia (routine of care) on

postoperative pain 48 hours after CRS-HIPEC surgery.

**Hypothesis:** Postoperative pain 48 hours after CRS-HIPEC surgery is not inferior with 4 quadrants TAP blocks (4Q-TAP) than Thoracic Epidural Analgesia (routine care).

c. **Secondary Aim 2:** To compare the total opioid consumption between patients with 4 quadrants TAP blocks (4Q-TAP) versus Thoracic Epidural Analgesia (routine care) intraoperatively and up to 48 hours after CRS-HIPEC surgery.

**Hypothesis:** Perioperative opioid consumption after CRS-HIPEC surgery is not higher in patients with 4 quadrants TAP blocks (4Q-TAP) than epidural analgesia (routine care).

d. **Secondary Aim 3:** To compare the length of stay (LOS) between patients with 4 quadrants TAP blocks (4Q-TAP) versus Thoracic Epidural Analgesia (routine care) after CRS-HIPEC surgery.

**Hypothesis:** The LOS after CRS-HIPEC surgery is shorter in patients with 4 quadrants TAP blocks (4Q-TAP) than Thoracic Epidural Analgesia (routine care).

e. **Secondary Aim 4.** To compare the incidence of adverse events (i.e. postoperative hypotension, failed block) related to 4 quadrants TAP blocks (4Q-TAP) versus Thoracic Epidural Analgesia (routine care) 48 hours after CRS-HIPEC surgery.

**Hypothesis:** The incidence of adverse events (i.e. postoperative hypotension, failed block) related to 4 quadrants TAP blocks (4Q-TAP) is lower than Thoracic Epidural Analgesia (routine care) 48 hours after CRS-HIPEC surgery.

f. **Secondary Aim 5.** To compare the incidence of opioid-related adverse (i.e. respiratory depression, pruritus, sedation, delirium) events related to 4 quadrants TAP blocks (4Q-TAP) versus Thoracic Epidural Analgesia (routine care) 48 hours after CRS-HIPEC surgery.

**Hypothesis:** The incidence of opioid-related adverse events is lower in patients receiving 4 quadrants TAP blocks (4Q-TAP) versus Thoracic Epidural Analgesia (routine care) 48 hours after CRS-HIPEC surgery.

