#### *4-quadrant TAP block*

**To enhance the analgesic efficacy of the traditional TAP block**, several authors have added a subcostal approach to provide analgesia to the upper half of the abdomen. In a cadaveric study of the four-quadrant TAP block (4QTAP), dermatomes T8-L1 were adequately covered with the solution of local anesthetic. Therefore, it was originally hypothesized that the 4QTAP block may be more beneficial in major abdominal surgery compared to the traditional TAP approach alone. In a prospective study of 124 patients, the surgical incision for abdominal surgery was within the dermatomal limits of the 4QTAP in 70% of patients. In a later study by Niraj et al, the authors demonstrated that 4QTAP with levobupivacaine resulted in similar pain scores and tramadol consumption when compared to epidural analgesia for laparoscopic colorectal surgery.

**The 4QTAP block may provide some advantages over epidural analgesia** as TAP blocks are associated with more stable hemodynamics and less use of vasopressor and intravenous fluids during and after surgery. In addition, 4QTAP blocks are not associated with postoperative urine retention neither the risk of epidural hematoma or infections. Lastly, the use of 4QTAP blocks can reduce the use of resources and personnel because there is no need for frequent monitoring of the epidural catheter and infusions pumps.

With the increased safety of ultrasound guided needle placement and 'real-time' visualization through dynamic scanning, **serious complications are rare** with the 4QTAP block. Needle puncture thru the peritoneum causing bowel or diaphragm perforation is unlikely, but is still a possibility. The abundance of structures in the peritoneal cavity makes the viewing of the needle in plane at all times during needle advancement of utmost importance. Lacerations of the liver have been reported during placement of right-sided TAP blocks. Abdominal wall hematoma, vascular injury, local anesthetic toxicity and are also potential, but rare complications.

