## **B. Interventions**

Patients will be randomized 1:1 on the morning of surgery to one of the following 2 interventions:

**TEAgroup:** Patients in this group will be treated as standard of care. An epidural catheter will be placed before induction of anesthesia by an anesthesiologist. The catheter will be placed between the thoracic vertebral spaces 8 and 12 according to routine care. A bolus or infusion of local anesthetic solution with or without the addition opioids will be given before surgical incision according to anesthesia provider's clinical judgment. If deemed appropriate, a pre-incision epidural bolus of hydromorphone (300-800 micrograms) may be administered according to the anesthesia provider's clinical judgment.

**4Q-TAP block group:** Patients in this group will have an ultrasound guided 4Q-TAP block. A maximum of 80 cc of a solution consisting of 30 mg of bupivacaine HCl in 10 cc of PFNS and 65 mg of liposomal bupivacaine in 10 cc of PFNS will be injected before surgical incision in each of the four quadrants.

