### **Adverse Event Definition**

An adverse event is any symptom, sign, illness, or experience which develops or worsens during the course of the study, whether or not the event is considered related to study drug. **Adverse events (AEs) related to the study interventions** will be recorded within the first 48 hours after the end of surgery. AEs related to the study will include postoperative hypotension needed pharmacological intervention including fluid resuscitation or temporary holding or discontinuation of epidural infusions, failed block (defined as patchy block or unilateral block needing pharmacological interventions or catheter removal), epidural space infection or abscess and epidural hemathoma.

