## **Primary Outcome Analysis**

## **Secondary Outcomes Analyses**

### **Safety**

***Safety will be summarized using*** the number and proportion of patients reporting any given event and will be tabulated by treatment received according to the worst severity experienced. Separate tables will be constructed for (a) all reported events, (b) procedure related events, (c) serious events. Event rates will be compared between treatment arms by Fisher's exact test.

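### The plan defines intervention-related adverse events in two ways, does not say which answers Aim 4, and tests the investigator-attributed version between arms

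*Combined protocol and SAP*

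**What the plan says.** Secondary Aim 4 (section 3, Study Aims) is directional: "The incidence of adverse events (i.e. postoperative hypotension, failed block) related to 4 quadrants TAP blocks (4Q-TAP) is lower than" with TEA, over 48 hours after surgery.

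Under Outcomes definitions in section 5, Adverse Event Definition specifies intervention-related events by a list, limited to the 48 hours after surgery ends: "AEs related to the study will include postoperative hypotension needed pharmacological intervention including fluid resuscitation", or pausing or stopping the epidural infusion; failed block; epidural infection or abscess; and epidural hematoma. Nobody has to decide whether the intervention caused the event.

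Adverse Events – General uses a different criterion. There an event is procedure-related when, "in the judgment of the Investigator; it is reasonable to believe that the event is associated with the assigned study procedure", and adverse events are monitored from the procedure to the end of the study.

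The Safety text under Secondary Outcomes Analyses says: "Separate tables will be constructed for (a) all reported events, (b) procedure related events, (c) serious events". It then plans Fisher's exact test to compare event rates between arms. The only definition of procedure-related in the document is the judgment-based one. Nothing under Secondary Outcomes Analyses mentions Aim 4.

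The synopsis title calls the trial "a single-blinded, randomized, non-inferiority study". The document does not say who is blinded and describes no blinded adjudication of events.

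**The concern.** The two definitions can classify the same patient differently. A 4Q-TAP patient with treated hypotension on the first postoperative day counts under the list. Under the other definition, that patient counts only if the investigator associates the event with the block.

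That judgment is made about the assigned procedure, so it can hardly be made without knowing the arm. The background sections also set expectations: hypotension is described as a drawback of epidural analgesia, while "TAP blocks are associated with more stable hemodynamics". An assessor who shares those expectations could attribute hypotension to the epidural in one arm and to the operation in the other. Any such difference would act in the direction Aim 4 predicts, and Fisher's test cannot separate a difference in attribution from a difference in events.

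At stake is a secondary safety comparison. The primary QoR-15 conclusion is not affected.

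**Working it through.** **The two definitions side by side**

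| | Adverse Event Definition (section 5) | Adverse Events – General |
|---|---|---|
| Criterion | Listed event | Investigator associates the event with the assigned procedure |
| Window | 48 hours after surgery | Procedure to end of study |
| Attribution step | None | Yes; no blinding of it described |
| Named in a planned between-arm test | Not by name | Yes, table (b), Fisher's exact test |
| Stated link to Aim 4 | None, but same events and window | None |

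The Study Event Schedule shows adverse event collection during surgery, at PACU discharge and on days 1 and 2. The windows may therefore be closer in practice than the wording suggests, but no text reconciles them.

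**Inputs from the documents.** The plan gives no rate, effect size or power for Aim 4, so there is no planned figure to reproduce. Allocation is 1:1. The synopsis gives 80 patients per arm; the Statistical Considerations give about 140 in total, or 70 per arm. The test is Fisher's exact test, with alpha and sidedness not stated for safety.

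**Assumptions, none from the documents.** Two-sided 0.05; the same true rate p of treated hypotension in both arms (20%, 30% or 40%); and a fraction a of those events judged procedure-related, which may differ by arm.

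**Formula.** Recorded counts are independent binomials, i ~ Bin(n, p·a_TEA) and j ~ Bin(n, p·a_TAP). The chance of a false advantage is

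P = Σ_i Σ_j Pr(i)·Pr(j), summed over pairs with j < i and Fisher p < 0.05.

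**One case.** n = 80 and p = 0.30 give 80 × 0.30 = 24 expected events per arm; 24 versus 24 has Fisher p = 1.0. With 80% and 40% attributed, the expected recorded counts are 24 × 0.8 = 19.2 and 24 × 0.4 = 9.6. The double sum gives P = 0.435.

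**Results: chance of a significant result favoring 4Q-TAP when true rates are equal**

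| Attributed, TEA vs 4Q-TAP | n per arm | p = 20% | p = 30% | p = 40% |
|---|---|---|---|---|
| No attribution step | 80 | 0.016 | 0.017 | 0.016 |
| 90% vs 75% | 80 | 0.049 | 0.070 | 0.095 |
| 90% vs 60% | 80 | 0.133 | 0.220 | 0.318 |
| 80% vs 40% | 80 | 0.269 | 0.435 | 0.602 |
| 90% vs 60% | 70 | 0.118 | 0.188 | 0.280 |
| 80% vs 40% | 70 | 0.228 | 0.382 | 0.530 |

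Equal attribution (90% in both arms) gives 0.016–0.017, so the problem is differing attribution rather than attribution itself. Moving the assumed fractions from 90% vs 70% to 90% vs 30% stretches the range at 80 per arm to 7–94%, so no single figure deserves weight.

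**Is the list itself neutral?** Not entirely. Its hypotension wording can be met by holding or stopping an epidural infusion, and its failed-block wording by catheter removal; only TEA patients can qualify by these routes. Suppose 30% in each arm have hypotension needing drugs or fluid, and a further 5, 10 or 15 percentage points of TEA patients qualify only by holding the infusion. Putting 0.35, 0.40 or 0.45 versus 0.30 into the same sum at 80 per arm gives 0.074, 0.215 and 0.437. Dropping attribution alone therefore does not restore 1.6–1.7%.

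**The case against.** The strongest reply is that the plan can be read as sound. The list sits under Outcomes definitions, names the two events Aim 4 names and shares its 48-hour window. The judgment-based definition sits in general reporting text that never mentions Aim 4. A reader might infer from the matching word *related* that Aim 4 will be tested on investigator-attributed events. The documents do not say so, and the list is the more natural reading.

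Nor is table (b) the only comparison. Safety is summarized as patients with each given event, so table (a) would show hypotension by arm whatever its cause. The reporting guidance generally leaves out blood pressure changes that need no treatment, so that row would mostly hold treated hypotension. Logistic regression is also planned for dichotomous outcomes. An attribution-free comparison would therefore stand beside table (b).

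Further, the definition of procedure-related continues with an unclear sentence about other products, techniques or medications contributing, which may widen what counts. Differential attribution is plausible but not shown: the background text describes expected effects, and that the assessor knows the arm is inferred.

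All of this stands, and it limits the point to an unresolved definition and one exposed test. It does not remove the point. Table (a) is neither limited to 48 hours nor assigned to Aim 4. If the Fisher tests in (a) and (b) disagree, nothing says which one answers the aim.

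**Conclusion.** The point holds as a gap in definition with a possible bias. Two definitions differ in criterion and stated window, neither is assigned to Aim 4, and the judgment-based one feeds a planned between-arm test without described blinded adjudication. If attribution differs by arm, that test can show a false advantage for 4Q-TAP.

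The size cannot be derived from the documents. The 13–60% illustration, against 1.6–1.7% without attribution, assumes 80 per arm, equal true rates of 20–40%, a two-sided 0.05 test, and attribution of 90% vs 60% or 80% vs 40%. At 70 per arm it is 12–53%.

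A reader might go further and infer that the trial will produce a false Aim 4 claim. The documents do not support that: they give no attribution data, do not tie Aim 4 to table (b), and provide an attribution-free table. This is worth correcting before analysis, as a secondary safety matter.

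**What to change.** Four statements in the outcome definitions and safety analysis would settle it.

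1. Aim 4 counts events meeting the section 5 list within 48 hours after surgery, in both arms, regardless of investigator attribution. Hypotension and failed block are tested separately, with alpha and sidedness stated.
2. The between-arm hypotension test counts only the criterion either arm can meet: hypotension needing pharmacological intervention, including fluid resuscitation. Epidural-only items (infusion held or stopped, catheter removal, epidural infection or abscess, epidural hematoma) are reported descriptively.
3. The failed-block comparison carries a caveat that its definition is partly worded around catheters.
4. Table (b), investigator-attributed events, is descriptive with no between-arm test.

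No new data should be needed, because the action taken is already to be recorded for each adverse event. There are two costs. Hypotension caused by surgery is counted in both arms, which slightly dilutes any true difference. A TEA patient whose hypotension was handled only by holding the infusion falls outside the tested count, so the descriptive count of such patients should be shown beside it.

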### **A. Setting and Population**

#### *Inclusion criteria:*

1. Written informed consent;
2. 18 years old or older;
3. American Society of Anesthesiologists physical status (ASA) 1-3;
4. Scheduled surgery: open elective CRS-HIPEC;
5. Able to complete the QoR 15 questionnaire;
6. Patients scheduled to receive intraoperative chemotherapy;

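### Non-serious chest pain and early headache are left out of the primary safety endpoint by default, even when the block or epidural is a suspected cause

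*Combined protocol and SAP*

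**What the plan says.** The list, in the Adverse Events section under General, opens: "For purposes of this study, the following events are not considered adverse events, because they are normally expected to occur in conjunction post-surgery". Three of its nine items matter here:

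- "Chest pain without associated ECG changes"
- "Post-anesthesia emesis, nausea, or headache (within 24 hours post-index procedure" hours being the only limit on that item
- "Electrolyte imbalance without clinical sequelae following endoscopic procedure, even if requiring correction"

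The paragraph after the list calls it guidance. It asks investigators to use their own judgement and allows them to report a listed event as an adverse event.

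The Synopsis defines the primary safety endpoint as "All reported adverse events". The inclusion criteria fix the operation: "Scheduled surgery: open elective CRS-HIPEC". Under Outcomes definitions, the Adverse Event Definition counts any new or worsening symptom or sign, related or not, and contains no exempt list.

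**The concern.** An exempt list is reasonable when it removes expected background events that say nothing about the treatments compared. It causes trouble when it also removes symptoms that the investigator suspects the study technique has caused, because the safety comparison exists to find those. Here the exemption depends only on the type of symptom. The chest-pain item has no limit on time, severity or cause, and the headache item is limited only by its post-anesthesia wording and the 24-hour window.

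At stake is the comparability of the arms on the primary safety endpoint. If a suspected block-related symptom is counted only when an investigator decides to count it, the reported rates depend partly on reporting habits, and those may differ by arm.

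**Working it through.** No arithmetic applies. The check sets the passages side by side and traces what happens to one kind of event.

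**1. Limits within the list.** Early pain is limited to 48 hours and to the incision or positioning. Emesis, nausea and headache are limited to 24 hours. Rhythm and blood-pressure changes are exempt only if untreated, and a fall in hematocrit only if there is no transfusion. Temperature has a ceiling. Chest pain is conditioned on the ECG alone. No item asks whether the block or epidural may be the cause.

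**2. Tracing a non-serious chest pain without ECG changes, or a headache within 24 hours, that the investigator suspects is due to the block or epidural.**

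| Place in the protocol | Result |
|---|---|
| Adverse Event Definition (Outcomes definitions) | Counts: any symptom or sign |
| Adverse Events, General: opening definition | Counts: any unwanted clinical event |
| Adverse Events, General: exempt list | Does not count |
| Procedure-related category (same section) | Defined as an adverse event judged related, so it presupposes that the event already counts |
| Investigator Reports, SAEs: 24-hour CRF reporting | Covers potentially procedure-related adverse events, with the same presupposition |
| Intervention-related harms named under Outcomes definitions | Treated hypotension, failed block, epidural infection or abscess, epidural hematoma; neither symptom is named |
| Data collection and measurements | Nausea and vomiting are collected separately; chest pain and headache are not |
| Safety tables (Secondary Outcomes Analyses) | Appears under all reported or procedure-related events only if it was reported |

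Two definitions bring the event in and the list takes it out. The remaining routes either presuppose that it counts or do not name it. It enters the endpoint only through the investigator's override.

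**3. The override.** It permits reporting but does not require it, and no criterion is attached. Suspected relation to the technique is not mentioned as a reason to use it.

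**4. Could it work differently by arm?** The title calls the trial single-blinded, and the documents do not say who is blinded. The interventions differ visibly: an epidural catheter placed before induction against four ultrasound-guided injections. Secondary Aim 4 hypothesises fewer related adverse events with 4Q-TAP. Event rates are then compared between arms by Fisher's exact test. Differential use is possible; nothing in the documents shows that it would occur.

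**5. Serious events.** The General section's definition begins "A serious adverse event (SAE) is defined as an event which leads to", so it starts from an event and does not require it to pass the list first. The same section requires every SAE to be reported. The reporting section repeats this whatever the attribution, Investigator Reports requires a CRF within 24 hours of awareness, and the safety analysis gives serious events their own table. Serious events are therefore captured. The list merely lacks a sentence saying that seriousness prevails.

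**6. The electrolyte item.** Every patient has open CRS-HIPEC, so an exemption for imbalance after an endoscopic procedure, read literally, never applies. The consequence would be extra reports in both arms, with no harm lost.

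**7. Time window.** The General section monitors adverse events to the end of the study, and follow-up is 30 days, so the chest-pain exemption can run that long. Outcomes definitions, however, records intervention-related events for 48 hours only, and the Study Event Schedule footnote lists surgery, PACU discharge and postoperative days 1 and 2. How far the missing time limit reaches depends on which window governs.

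**The case against.** The strongest reply is that the list is guidance, that investigators are told to use judgement, and that real injuries are caught elsewhere. Much of this stands. The list exempts certain symptoms, not injuries: a perforation, hematoma or abscess is still an adverse event. The harms named under Outcomes definitions are recorded regardless, and complications are recorded on the Clavien-Dindo scale and POMS. The blood-pressure exemption covers only untreated changes, so it does not contradict the treated-hypotension event.

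The reply does not close the gap for non-serious symptoms, because the override has no criterion and the procedure-related routes presuppose adverse-event status.

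A reader might infer several stronger things that the documents do not support:

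- *That serious events are lost, for example a readmission for chest pain.* The SAE rules in step 5 above capture them.
- *That signs of block harm in general leave the endpoint.* Only non-serious exempted symptoms do, and only by default.
- *That these symptoms mark particular complications.* The background says "Needle puncture thru the peritoneum causing bowel or diaphragm perforation is unlikely, but is still a possibility" but links no symptom to it, and nothing in the documents links headache to epidural placement. The case for an exception rests on suspected relation and needs neither link.
- *That the whole list was written for endoscopy.* One item of nine carries that wording.

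**Conclusion.** The point holds for non-serious chest pain without ECG changes and for post-anesthesia headache within 24 hours when the block or epidural is a suspected cause. These are excluded by default and enter the primary safety endpoint only at unguided discretion, and the list contradicts the definition under Outcomes definitions. The electrolyte wording does not fit this trial's surgery.

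The size is unknown because the documents give no event rates. One could note that a single event is 1/80 = 1.25% to 1/70 = 1.43% of an arm (80 per arm in the Synopsis, 140/2 = 70 from the sample-size table). That is true of any unrecorded event and does not measure the effect of this list.

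Concern about differential reporting assumes that whoever decides what to report may know the allocation, which the documents neither confirm nor exclude. The QoR-15 primary analysis is not affected. The matter is worth correcting because it concerns the primary safety endpoint and takes one clause to resolve.

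**What to change.** In the exempt list under Adverse Events, General:

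1. Add a sentence saying that the list does not apply to any event that meets an SAE criterion or is possibly related to the block, the epidural or the study drug. This also supplies the missing statement that seriousness prevails.
2. In the electrolyte item, replace the reference to an endoscopic procedure with the trial's own surgery.
3. Reconcile the list with the Adverse Event Definition under Outcomes definitions, so that one definition governs what enters the primary safety endpoint.

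With the first change in place, deleting the chest-pain item or narrowing the headache item is optional. The cost is a wording amendment, matching guidance on the case report form, and probably a few more adverse-event reports. Without event rates, that number cannot be estimated.
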